## 5.5. Concomitant Treatments

### 5.5.1. Acceptable Concomitant Medications

All treatments that the investigator considers necessary for a subject's welfare may be administered at the discretion of the investigator in keeping with the community standards of medical care. All concomitant medication will be recorded on the eCRF including all prescription, over-the-counter (OTC), herbal supplements, and IV medications and fluids. If changes occur during the trial period, documentation of drug dosage, frequency, route, and date will also be included on the eCRF.

Palliative and supportive care is permitted during the course of the trial for underlying medical conditions and management of symptoms.

Surgery for tumor control or symptom management is not permitted during the study. Palliative radiotherapy is permitted to a single lesion if considered medically necessary by the treating physician as long as the lesion is NOT a RECIST 1.1-defined target lesion and treatment is NOT administered for tumor control. Trial therapy should be held during the course of palliative radiotherapy and should be resumed no earlier than the next scheduled administration of trial therapy. The specifics of the radiation treatment, including the location, will be recorded.

All concomitant medications received within 30 days before the first dose of trial treatment through the Safety Follow-up Visit should be recorded.

#### 5.5.1.1. Rescue Medications and Supportive Care

Subjects should receive appropriate supportive care measures as deemed necessary by the treating investigator including but not limited to the items outlined below.

For guidelines for continuing treatment with AGEN2034, see [Section 5.4.4.2.2](#).

- **Diarrhea:** Subjects should be carefully monitored for signs and symptoms of enterocolitis (such as diarrhea, abdominal pain, blood or mucus in stool, with or without fever) and of bowel perforation (such as peritoneal signs and ileus). In symptomatic subjects, infectious etiologies should be ruled out, and if symptoms are persistent and/or severe, endoscopic evaluation should be considered. All subjects who experience diarrhea should be advised to drink liberal quantities of clear fluids. If sufficient oral fluid intake is not feasible, fluid and electrolytes should be substituted via IV infusion.
- **Anemia:** Transfusions and/or erythropoietin may be utilized as clinically indicated for the treatment of anemia, but should be clearly noted as concurrent medications. Consider a potential immunologic etiology.
- **Neutropenia:** Prophylactic use of colony-stimulating factors including Granulocyte Colony- Stimulating Factor (G-CSF), PEGylated G-CSF or Granulocyte Macrophage Colony- Stimulating Factor GM CSF is not allowed in this trial. Therapeutic use of

G-CSF is allowed in subjects with Grade 3-4 febrile neutropenia. Consider a potential immunologic etiology.

- Thrombocytopenia: Transfusion of platelets may be used if clinically indicated. Immune thrombocytopenia purpura (ITP) should be ruled out before initiation of platelet transfusion.
- Anti-infectives: Subjects with a documented infectious complication should receive oral or IV antibiotics or other anti-infective agents as considered appropriate by the treating Investigator for a given infectious condition, according to standard institutional practice.
- Adverse event with a potential immunologic etiology (irAE): identification, evaluation and management of adverse experiences of a potential immunologic etiology. Depending on the type and severity of an irAE, oral or intravenous treatment with a corticosteroid should be considered, in addition to appropriate symptomatic treatment of a given condition (see [Section 5.6](#) for management algorithms). These are also considered AEs of special interest (AESI) and should be reported to the Sponsor per [Section 7.2.2.2](#).

### **5.5.2. Prohibited and/or Restricted Treatments**

As stated in the exclusion criteria ([Section 4.3](#)), subjects must not have had chemotherapy, radiotherapy (other than palliative bone-directed radiotherapy, as described in [Section 5.5.1](#)), major surgery, or received another investigational agent within 28 days before the start of study treatment.

Subjects are prohibited from receiving the following therapies and treatments during the Screening and Treatment periods of this trial:

- Immunotherapy not specified in this protocol.
- Chemotherapy.
- Investigational agents other than AGEN2034.
- Surgery for symptom management or tumor control.
- Growth factors (granulocyte colony-stimulating factor or granulocyte macrophage colony- stimulating factor). Exception: Erythropoietin and darbepoietin alpha may be prescribed at the investigator's discretion. Therapeutic use of G-CSF is allowed in subjects with Grade 3 or 4 febrile neutropenia.
- Radiation therapy for tumor control.
- Glucocorticoids for any purpose other than to modulate symptoms from an irAE, or for use as a pre-medication in subjects with a known history of an IV contrast allergy administered as part of computed tomography (CT) radiography.

Note: Replacement doses of corticosteroids (for example, prednisone 5-7.5 mg daily) are permitted while on study.

Note: Use of inhaled or topical corticosteroid is permitted.

- Bisphosphonates and/or receptor activator of nuclear factor kappa-B ligand (RANKL) inhibitor therapies cannot be initiated after informed consent has been signed. These therapies may be continued IF treatment with an agent from one of these two classes was initiated PRIOR to signing informed consent.
- Subjects who, in the assessment by the investigator, require the use of any of the aforementioned treatments for clinical management should be removed from the trial.
- Subjects may receive other medications that the investigator deems to be medically necessary.
- Medications listed in the Exclusion Criteria are prohibited in this trial.
- There are no prohibited therapies during the Post-Treatment Follow-up Phase

### **5.5.3. Other Restrictions and Precautions**

The following non-drug therapies must not be administered or performed during the study (and within 28 days before the start of trial treatment):

- Major surgery (excluding prior diagnostic biopsy).
- Herbal remedies with immunostimulating properties (e.g., mistletoe extract) or that are known to potentially interfere with major organ function (e.g., hypericin).
- Subjects should not abuse alcohol or other drugs during the study.

## **5.6. Management of Immune-related Adverse Events**

Immuno-oncology agents such as AGEN2034 are associated with irAEs. Early recognition and management of irAEs may mitigate severe toxicity. Investigators should also monitor subjects closely for potential irAEs, which may manifest at the earliest after weeks of treatment. Such events may consist of persistent rash, diarrhea, colitis, autoimmune hepatitis, pneumonitis, encephalitis, arthritis, glomerulonephritis, cardiomyopathy, or uveitis and other inflammatory eye conditions.

Management Algorithms have been developed to assist investigators in assessing and managing the following groups of irAEs: Gastrointestinal, Pulmonary, Dermatological, Renal, Hepatic, Neurological, and Endocrine among others.

Adverse events (both non-serious and serious) associated with drug exposure and consistent with an immune phenomenon may represent an immunologic etiology. These immune related AEs may be predicted based on the nature of the study drugs, their mechanism of action, and reported experience with immunotherapies that have a similar mechanism of action. An irAE can occur shortly after the first dose or several months after the last dose of study drug. Particular attention should be paid to AEs that may be suggestive of potential irAEs as outlined below.

Immune-related AEs are considered are considered AESIs and should be reported to the Sponsor per [Section 7.2.2.2](#).

### 5.6.1. Dermatological Immune-related Adverse Events

Rule out non-inflammatory causes, if non-inflammatory cause is identified, treat accordingly and continue therapy per protocol.

**Table 4: Dermatological Immune-related Adverse Event Management Algorithm**

Dermatological Immune-related Adverse Events		
Grade of Rash (NCI CTCAE v4.03)	Management	Follow-Up
Grade 1–2 Covering ≤30% body surface area.	
 
• Symptomatic therapy (e.g., antihistamines, topical corticosteroids).
 
• Continue AGEN2034 therapy per protocol.
 
	
 
• If persists >1 to 2 weeks or recurs: Consider skin biopsy.
 
• Delay AGEN2034 therapy.
 
• Consider 0.5–1 mg/kg/day methylprednisolone IV or oral equivalent. Once improving, taper corticosteroids over at least 1 month; consider prophylactic antibiotics for opportunistic infections; and resume AGEN2034 therapy per protocol.
 
• If worsens: treat as Grade 3–4.
 

Grade 3–4 Covering >30% body surface area; life-threatening consequences.	
 
• Delay or discontinue AGEN2034 therapy per protocol.
 
• Consider skin biopsy.
 
• Dermatology consult
 
• 1–2 mg/kg/day methylprednisolone IV or oral equivalent.
 
	
 
• If improves to Grade 1: taper corticosteroids over at least 1 month; add prophylactic antibiotics for opportunistic infections.
 
• Resume AGEN2034 therapy per protocol.
 

### 5.6.2. Gastrointestinal Immune-related Adverse Events

Rule out non-inflammatory causes, if non-inflammatory cause is identified, treat accordingly and continue therapy. Opiates/narcotics may mask symptoms of perforation. Infliximab should not be used in cases of perforation or sepsis.

**Table 5: Gastrointestinal Immune-related Adverse Event Management Algorithm**

Gastrointestinal Immune-related Adverse Events		
Severity of Diarrhea/Colitis (NCI CTCAE v4.03)	Management	Follow-Up
Grade 1  Diarrhea: <4 stools/day over baseline.  Colitis: asymptomatic.	
 
Continue AGEN2034 therapy per protocol.
 
Symptomatic treatment
 
	
 
Close monitoring for worsening symptoms.
 
Educate subject to report worsening immediately.
 
Consider symptomatic treatment including hydration, electrolyte replacement, dietary changes (e.g. American Dietetic Association colitis diet), and loperamide
 
If worsens: treat as Grade 2 or 3–4.
 

Grade 2  Diarrhea: 4–6 stools per day over baseline; IV fluids indicated <24 h; not interfering with activities of daily living (ADL).  Colitis: abdominal pain; blood in stool	
 
Delay AGEN2034 therapy per protocol.
 
Symptomatic treatment.
 
	
 
If improves to Grade 1: resume AGEN2034 therapy per protocol.
 
If persists >5 to 7 days or recurs: 0.5–1 mg/kg/day methylprednisolone or equivalent.
 
When symptoms improve to Grade 1, taper corticosteroids over at least 1 month; consider prophylactic antibiotics for opportunistic infections; resume AGEN2034 therapy per protocol.
 
If worsens or persists >3 to 5 days with oral corticosteroids: treat as Grade 3–4.
 

Grade 3 to 4  Diarrhea (Grade 3): ≥7 stools per day over baseline; incontinence; IV fluids ≥24 h; interfering with ADL.  Colitis (Grade 3): severe abdominal pain, medical intervention indicated, peritoneal signs.  Grade 4: life-threatening, perforation	
 
Discontinue AGEN2034 therapy per protocol.
 
1–2 mg/kg/day methylprednisolone IV or equivalent.
 
Add prophylactic antibiotics for opportunistic infections.
 
Consider lower endoscopy.
 
	
 
If improves: continue corticosteroids until Grade 1, then taper over at least 1 month.
 
If persists >3 to 5 days, or recurs after improvement: add infliximab 5 mg/kg (if no contraindication). Note: infliximab should not be used in cases of perforation or sepsis.
 

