## 5.4.4. Dose Modifications and Treatment Delay

### 5.4.4.1. Dose Reductions

**No AGNE2034 dose reduction or escalation is allowed.** Each subject will stay on the dose levels assigned in the trial unless treatment needs to be stopped.

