#### 5.4.4.2.2. *Criteria to Resume Treatment*

Subjects may resume treatment with AGEN2034 when drug-related AE(s) resolve(s) to Grade 1 or baseline value, with the following exceptions:

- Subjects may resume treatment in the presence of Grade 2 fatigue.
- Subjects who have not experienced a Grade 3 drug-related skin AE may resume treatment in the presence of Grade 2 skin toxicity.

- Subjects with baseline Grade 1 AST/ALT or total bilirubin who require dose delays for reasons other than a 2-Grade shift in AST/ALT or total bilirubin may resume treatment in the presence of Grade 2 AST/ALT or total bilirubin.
  - Subjects with combined Grade 2 AST/ALT AND total bilirubin values meeting discontinuation parameters ([Section 4.4.1](#)) should have treatment permanently discontinued.
- Drug-related pulmonary toxicity, diarrhea, or colitis must have resolved to baseline before treatment is resumed.
- Drug-related endocrinopathies adequately controlled with only physiologic hormone replacement may resume treatment.
- Subjects who received systemic corticosteroids for management of any drug-related toxicity must be off corticosteroids or have tapered down to an equivalent dose of prednisone  $\leq$  10 mg/day.

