**Table 7: Hepatic Immune-related Adverse Event Management Algorithm**

Hepatic Immune-related Adverse Events		
Grade of Liver Test Elevation (NCI CTCAE v4.03)	Management	Follow-Up
Grade 1 AST or ALT >ULN to 3 x ULN and/or total bilirubin >ULN to 1.5 x ULN.	
 
Continue AGEN2034 therapy per protocol.
 
	
 
Continue liver function tests (LFT) monitoring per protocol.
 
If worsens: treat as Grade 2 or Grade 3–4.
 

Grade 2 AST or ALT >3 to ≤5 x ULN and/or total bilirubin >1.5 to ≤3 x ULN.	
 
Delay AGEN2034 therapy per protocol.
 
Increase frequency of monitoring to every 3 days.
 
If subject has concurrent AST or ALT > 3 x ULN AND total bilirubin > 2 x ULN, Discontinue AGEN2034 therapy per protocol.
 
	
 
If returns to baseline: resume routine monitoring; resume AGEN2034 therapy per protocol.
 
If elevations persist >5 to 7 days or worsen: 0.5–1 mg/kg/day methylprednisolone IV or oral equivalent. When LFT returns to Grade 1 or baseline, taper corticosteroids over at least 1 month, consider prophylactic antibiotics for opportunistic infections, and resume AGEN2034 therapy per protocol.
 

Grade 3–4 AST or ALT >5 x ULN and/or total bilirubin >3 x ULN.	
 
Discontinue AGEN2034 therapy per protocol.
 
Increase frequency of monitoring to every 1–2 days.
 
1–2 mg/kg/day methylprednisolone IV or oral equivalent*.
 
Add prophylactic antibiotics for opportunistic infections.
 
Consult gastroenterology.
 
Consider obtaining MRI/CT scan of liver and liver biopsy if clinically warranted.
 
	
 
If returns to Grade 2: taper corticosteroids over at least 1 month.
 
If does not improve in > 3 to 5 days, worsens or rebounds: add mycophenolate mofetil 1 g twice daily. If no response within an additional 3–5 days, consider other immunosuppressants per local guidelines.
 

\*The recommended starting dose for Grade 4 hepatitis is 2 mg/kg/day methylprednisolone IV.

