**Table 10: Neurological Immune-related Adverse Event Management Algorithm**

Neurological Immune-related Adverse Events		
Grade of Neurological Toxicity (NCI CTCAE v4.03)	Management	Follow-Up
Grade 1 Asymptomatic or mild symptoms; intervention not indicated.	
 
Continue AGEN2034 therapy per protocol.
 
	
 
Continue to monitor subject.
 
If worsens: treat as Grade 2 or Grade 3-4.
 

Grade 2 Moderate symptoms; Limiting instrumental activities of daily life (ADL).	
 
Delay AGEN2034 therapy per protocol.
 
Treat symptoms per local guidelines.
 
Consider 0.5 to 1.0 mg/kg/day methylprednisolone IV or oral equivalent.
 
	
 
If returns to baseline: resume AGEN2034 therapy per protocol.
 
If worsens: treat as Grade 3-4.
 

Grade 3-4 Severe symptoms; Limiting self-care activities of daily life; Life-threatening.	
 
Discontinue AGEN2034 therapy per protocol.
 
Obtain neurology consult.
 
Treat symptoms per local guidelines.
 
1.0 to 2.0 mg/kg/day methylprednisolone IV or IV equivalent.
 
Add prophylactic antibiotics for opportunistic infections.
 
	
 
If improves to Grade 2: taper corticosteroids over at least 1 month.
 
If worsens or atypical presentation: consider IV immunoglobulin or other immunosuppressive therapies per local guidelines.
 

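### Table 5 prints Grade 1 as the trigger to restart AGEN2034 after Grade 2 diarrhea or colitis, while the governing Section 5.4.4.2.2 requires resolution to baseline

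*Protocol*

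**What the plan says.** Section 5.4.4.2.2 of the protocol sets a general rule that dosing may resume once a drug-related event is back to Grade 1 or baseline, and then lists exceptions. One is "Drug-related pulmonary toxicity, diarrhea, or colitis must have resolved to baseline before treatment is resumed".

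Table 5 (Section 5.6.2) delays AGEN2034 for Grade 2 diarrhea or colitis and gives two routes back to treatment:

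- Without steroids: "If improves to Grade 1", resume per protocol.
- After steroids, started if the event lasts more than 5 to 7 days or recurs: "When symptoms improve to Grade 1, taper corticosteroids over at least 1 month; consider prophylactic antibiotics for opportunistic infections; resume AGEN2034 therapy per protocol".

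Neither route mentions baseline or cites Section 5.4.4.2.2.

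Three other provisions bear on which text controls. Section 5.4.4.2.1 keeps a delayed dose on hold until the retreatment criteria are met. Section 5.5.1.1 directs the reader to Section 5.4.4.2.2 with the words "For guidelines for continuing treatment with AGEN2034, see". Section 5.6 describes the tables as aids: "Management Algorithms have been developed to assist investigators".

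**The concern.** Diarrhea and colitis are expressly taken out of the general restart rule, yet Table 5 prints that rule's Grade 1 threshold for them. A site working from the table sees a specific symptom level followed by an instruction to resume. If it checks only the opening sentence of Section 5.4.4.2.2, it finds Grade 1 or baseline there too, which seems to confirm the table. The exception appears several bullets further down.

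What is at stake is re-exposure while immune-related bowel toxicity is unresolved, and different handling of the same event across the approximately 60 Phase 2 centers. Section 1.1.3.2 reports occasional recurrence of immune-mediated events when nivolumab was restarted, and Section 1.1.2.2 treats nivolumab as the best guide to AGEN2034 safety. Under Section 4.4.1, drug-related Grade 3 diarrhea or colitis of any duration ends treatment.

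**Working it through.** The plan states no figure on this point, so the check sets the texts side by side.

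**Same events.** Table 5 covers immune-related diarrhea and colitis. Section 2.2 describes immune-related events as drug-related. Section 5.4.4.2.2 covers drug-related diarrhea and colitis. The scopes therefore match.

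**Grade 1 is not baseline.** Table 5 defines Grade 1 diarrhea as fewer than 4 stools a day over baseline and Grade 2 as 4 to 6. In whole stools, Grade 1 is 1, 2 or 3 above baseline, and resolution to baseline is 0 above. The gap between the two triggers is 1–3 stools a day.

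**Outcome after a Grade 2 delay, no steroids given:**

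| Stools/day over baseline | Table 5 printed trigger | Section 5.4.4.2.2 |
|---|---|---|
| 4–6 | hold | hold |
| 1–3 | resume | hold |
| 0 | resume | resume |

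The texts part only in the middle row. An event that never exceeds Grade 1 stays on drug under both: Table 5 continues treatment at Grade 1, and Section 5.4.4.2.1 delays from Grade 2.

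**Colitis.** Table 5 defines Grade 1 colitis as asymptomatic. Neither text says how to tell asymptomatic colitis from baseline, so no size can be put on the gap there.

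**After steroids.** The conflict is milder. Grade 1 first starts a taper of at least 1 month, and resumption comes last. Grade 1 is still the only symptom level named before resumption.

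**Pulmonary toxicity.** It stands in the same sentence of Section 5.4.4.2.2. The Grade 2 row of Table 6 starts the taper when symptoms are near baseline and then resumes per protocol. That too is looser than resolved to baseline, again with a taper of at least 1 month in between.

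**The case against.** The strongest reply is that the protocol already resolves this. Table 5 says per protocol, Section 5.4.4.2.1 requires the retreatment criteria to be met, Section 5.5.1.1 points to Section 5.4.4.2.2, and Section 5.6 gives the tables an assisting role. A site would have to overlook all of these to restart too early. Subjects are also assessed for possible events of special interest before each dose (Section 7.1.8), and the investigator may delay for any event. The protocol accepts dosing at Grade 1 when an event never went higher.

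Most of this stands. A reader might infer that two binding rules compete. They do not: Section 5.4.4.2.2 governs. But deferring to another section does not correct a specific threshold printed in the table. Nor does tolerance of Grade 1 from the outset answer the point, because the protocol chose a stricter test for restarting after Grade 2.

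Two further inferences are tempting and should not be drawn.

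- *That the looser trigger is clearly a slip.* The first Grade 2 follow-up step in Table 10 does read "If returns to baseline", and Table 7 likewise waits for baseline before "resume routine monitoring; resume AGEN2034 therapy per protocol", although Section 5.4.4.2.2 sets no baseline requirement for neurological events or liver tests. But Table 9 resumes from Grade 1, Table 6 says near baseline, and Table 7's own steroid step accepts Grade 1 or baseline. The tables vary too much to show intent.
- *That full-dose restart adds to the discrepancy.* Section 5.4.4.1 says "Each subject will stay on the dose levels assigned in the trial unless treatment needs to be stopped". The restart dose, 3 mg/kg in Phase 2, is therefore the same under either text. Only the timing differs.

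**Conclusion.** The inconsistency is real and lies in current text. Its size is a restart at 1–3 stools a day above baseline where the governing rule allows none. It is confined to events that reached Grade 2 and were delayed. How many subjects this would touch cannot be derived from the documents.

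The conclusion assumes that Section 5.4.4.2.2 states the intended rule, which its governing position supports. If the sponsor in fact intends Grade 1, Section 5.4.4.2.2 is the text to amend. Either way the two should agree.

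A reader might look for an effect on the trial's result. The documents support none on the primary response endpoint, sample size or power. This is an inconsistency in dosing instructions, worth correcting at the next amendment.

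**What to change.** In the Grade 2 follow-up cell of Table 5:

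1. First step: *at Grade 1, continue to hold AGEN2034 with symptomatic treatment and monitoring; restart only after resolution to baseline (Section 5.4.4.2.2).*
2. Start of the steroid step: *if Grade 2 persists beyond 5 to 7 days or recurs.* Simply replacing Grade 1 with baseline in the first step would leave a subject at Grade 1 but above baseline with no stated branch. The steroid step could then be read as calling for methylprednisolone 0.5–1 mg/kg/day for residual Grade 1 symptoms.
3. End of the steroid step: *restart only when Section 5.4.4.2.2 is satisfied, meaning resolved to baseline and either off corticosteroids or at no more than 10 mg/day prednisone or equivalent.*

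In the Grade 2 row of Table 6, keep near baseline as the point at which the taper starts, and make the restart conditional on the same Section 5.4.4.2.2 criteria.

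The changes go into a protocol amendment (Section 10.1), with a reminder to sites in the meantime. Some subjects will restart later. A few may reach the limit of more than 6 weeks without dosing in Section 4.4.1, with the investigator–sponsor consultation in Section 6.4.1.11. The existing text already implies both costs. Visits, sample size and analysis do not change.
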